## **8. Adverse events management**

### **8.1 Adverse events in the current study**

The current study aims to measure implementation of a cardiovascular CPR and its impact on chest pain management in primary care. We will measure several endpoints in both intervention and control group. We therefore expect some minor changes in GPs behaviour regarding investigations and diagnostic approach, as those using the CPR will be provided with additional information concerning patient's risk of cardiogenic chest pain. Those changes will be measured during follow-up.

To avoid misuse of the CPR, GPs selected to use the CPR will undergo intensive training (see Annex 1). Moreover, except calculating the risk of cardiogenic chest pain, GPs are asked to take care of patients according to their scientific knowledge and clinical experience. We therefore do not expect any adverse event due to the CPR itself for patients included in the trial.

### **8.2 Monitoring of adverse events**

Intermediate analysis is done at 3 months after patients index visit to display any unexpected effect of the CPR. In case of unfavourable effect for patients included, study will be immediately stopped. For stopping rules, please refer to *Chapter 3.4*.

## **9. Quality control and assurance**

### **9.1 Monitoring**

Follow-up will last 6 to 9 months, with intermediate analysis at 3 months. To insure the data collection and avoid loss of follow-up, a member of research team will phone patients at 3 months and will also contact GPs at 9 months to insure closing of the follow-up.

*Quality control* will be provided by an independent GP and a hospital internist not aware of the current study. They will both review 20% of the cases, randomly

selected, to insure correct management of patients and validity of the data collected before analysis. Both reviewing and follow up should certify as surely as possible and without any invasive procedure the correct diagnosis and management of patients' complaint.

## 9.2 Audit and inspection

This trial, as an implementation study of a CPR, does not involve any treatment or drug. Audit and inspection are therefore not strictly required.

## 10. Statistics

[figure not shown]
### 10.1 Number of subjects

Calculation of the number of subjects is based upon the TOPIC study, targeting the same population of patients with chest pain. We used a sample size calculation table for cluster-randomized trial to calculate the number of clusters needed with different values of subjects per cluster ( $m$  value). Calculation has been made for different variables up to the endpoints of the study. We chose the following variables for the calculation of the number of subjects: number of paraclinical tests, number of referral to specialist, number of hospitalisations.

[figure not shown]
All the true proportions for each variable in the control arm of the sample size calculation table come from the TOPIC study results. We then decided a reasonable decrease expected in the rate of paraclinical tests, referral and hospitalisations while using the CPR, which led us to the expected proportions in the intervention arm

In the TOPIC study, investigators reported 42% (284/672) of patients with paraclinical tests, 16% (110/672) with referral to specialist and 8% (53/672) hospitalised up to 12 months of follow-up (2).

To choose the number of cluster needed in each arm of the trial we took a coefficient of variation of 0.2. Final decision about number of subjects per cluster and number of clusters was based upon practical considerations so that recruitment procedure remains comfortable for GPs and to limit its duration.

Based upon the results shown above, we chose a number of 150 GPs in each arm, with 50 patients per cluster, so that the power of the study is sufficient to get a difference in paraclinical tests. We therefore need a total amount of 300 GPs, each of them recruiting 50 patients complaining of chest pain, leading us to a total amount of 15,000 patients.

Duration of inclusion is also calculated upon the TOPIC study in which chest pain occurred in 672 cases among 24,620 consultations during 300 weeks. We can therefore expect 2 to 3 patients with chest pain per week on the average, which leads us to an inclusion period of about 6 months for GPs to enrol the 50 patients needed.

N.B. This is an estimation based on the TOPIC study, which was run in the same target population of GPs as the current trial. This may eventually lead to a bias, as they were aware of chest pain as the purpose of the study. Investigators may therefore decide to run a Baseline Survey among Swiss GPs to verify true proportions before starting with the proper implementation study.

## 10.2 Data analysis

- a) Sampling and characteristics of GPs recruited (+/- Baseline Survey)
- b) Patients characteristics in usual practice group versus CPR group (age, sex, personal history of cardiovascular disease, cardiovascular risk factors, emergency consultation, telephonic interview, home visit, chest pain as main or secondary complaint)
- c) Patients characteristics within CPR group: low-risk versus high-risk of cardiogenic chest pain

- d) Impact of the CPR within CPR group

	CPR < 5 points (low risk)	CPR 5 to 7 points (intermediate risk)	CPR > 7 points (high risk)
Extra investigations			
Referral			
Patient's outcome			

- e) CPR calculated *a posteriori* in usual practice group, endpoints values and comparison of endpoints in low risk patients of usual practice group versus CPR group
- f) CPR group versus usual practice group

	CPR	Usual practice
Extra investigations		
Referral		
Patient's outcome		

- g) Implementation: use/non use rate of the CPR, acceptability and satisfaction.

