### 3.5 Data collected in the CRF

A case report form (CRF) has to be filled in by all the GPs for each patient included to define patient's characteristics, current pain, personal history of cardiovascular disease and risk factors. It will also provide investigators with information regarding complementary investigations, referrals or hospitalizations for each patient at the time of index visit.

GPs of the intervention group will be asked to calculate the risk of cardiogenic chest pain for each patient with the CPR. The CRF also includes questions directly addressed to GPs to appreciate use, satisfaction and acceptability of the CPR.

GPs who belong to the usual care group will have to evaluate the risk of cardiogenic chest pain according to their clinical judgement only.

As all the items of the CPR are part of usual practice (patient's history and physical examination) investigators will be able to calculate patients' risk of cardiogenic chest pain a posteriori in the usual care group with the data collected in the CRF.

[figure not shown]
(See Annex 2 for complete CRF)

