## 5. Study CPR

GPs selected to use the cardiovascular CPR as an assistive tool will have to calculate the risk of cardiac origin to chest pain for each patient. According to Gencer and al. (8), the Swiss CPR is the following:

Swiss Heart Score	
Men over 55 years, women over 65 years	2 points
Known cardiovascular risk	2 points
Personal history of cardiovascular disease	2 points
Substernal pain	2 points
Duration of pain from 1 to 60 minutes	1 point
Increasing with effort	1 point
No tenderness at palpation	1 point
Total < 5 points: low risk of cardiogenic chest pain	
Total 5 to 7 points: intermediate risk of cardiogenic chest pain	
Total > 7 points: high risk of cardiogenic chest pain	
- Sensitivity 97.6%, specificity 71.3%, negative likelihood ratio 0.033, negative predictive value 99.5% (derivation cohort)	
- Sensitivity 85.6%, specificity 47.2%, negative likelihood ratio 0.305, negative predictive value 94.8% (validation cohort)	

Except filling in the CRF and – for GPs allocated to the intervention group - calculating the risk of cardiogenic chest pain, taking history of the patient, examination, and further investigations have to be done as usual by GPs, according to their scientific knowledge and clinical experience.

Intensive training will provide GPs of the intervention group all information concerning aim, performance and limitations of the cardiovascular CPR as an assistive, prognostic tool (see Annex 1). Diagnosis and treatments should not be altered.

N.B. Investigators may choose to use the Marburg Heart Score instead of the Swiss Heart Score according to the not yet published results of Marburg's last external validation study. This will be decided before submission of the current protocol to the ethical committee.

Marburg Heart Score	
Men over 55 years, women over 65 years	1 point
Known clinical vascular disease*	1 point
Pain worse during exercise	1 point
Pain not reproducible by palpation	1 point
Patient assumes pain is of cardiac origin	1 point
Total ≤ 2 points: low risk of cardiogenic chest pain	
* Coronary artery disease, occlusive vascular disease or cerebrovascular disease	
Sensitivity 89.1%, specificity 63.5%, negative likelihood ratio 0.17, negative predictive value 97.9% (results to be published)	

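### The score-group analyses in section 10.2 give no like-for-like comparison of the arms: d) has no control column, and e) stops below 5 points and, as described, scores the two arms by different methods

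*Protocol*

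**What the plan says.** Protocol section 10.2 lists three analyses that bear on the effect of the rule.

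- Item d), headed "Impact of the CPR within CPR group", has columns for below 5, 5 to 7 and above 7 points. All of them are in the CPR arm.
- Item e) has the score worked out afterwards in usual care, with endpoint values, and then a "comparison of endpoints in low risk patients of usual practice group versus CPR group". Section 5 defines that group: "Total < 5 points: low risk of cardiogenic chest pain".
- Item f) is "CPR group versus usual practice group" on investigations, referrals and outcome, with no restriction by score.

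Section 3.5 gives the source of the score in each arm. In the CPR arm, "GPs of the intervention group will be asked to calculate the risk of cardiogenic chest pain for each patient with the CPR". For the other arm, "investigators will be able to calculate patients' risk of cardiogenic chest pain a posteriori in the usual care group" from the CRF data. No investigator calculation is described for the CPR arm. The CRF (Annex 2) has a score box with a total for CPR-arm GPs only. It also asks them whether they used the score during the consultation and, if not, whether they forgot it or found it unsuitable.

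**The concern.** There are three linked problems.

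1. **Item d) is not a measure of impact.** Section 11.1 says that GPs already use every item of the rule in ordinary practice. Tests and referrals should therefore rise with the score in usual care too. Without a control column, that gradient cannot be separated from an effect of the rule.
2. **Item e) names no comparison between arms at 5 points or more.** Annex 1 tells CPR-arm GPs to investigate further when the score and their impression disagree, so testing could change above the cut-off as well as below it. If a saving below 5 points were offset above it, f) would show little net difference and no listed comparison would explain why.
3. **Membership of the low-risk group is decided differently in the two arms.** In usual care the investigators score from CRF items. In the CPR arm, on the plain reading, the GP's total decides. A CPR patient without a total cannot be placed, and the last step in section 10.3 for missing data is exclusion. Loss of this kind occurs after randomisation, in one arm only, and may be related to how the patient was managed.

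**Working it through.** **Inputs from the protocol.** CHD prevalence p = 12% (section 1.1). Swiss score at the cut-off of 5 (section 5): derivation cohort, sensitivity Se 97.6% and specificity Sp 71.3%; validation cohort, Se 85.6% and Sp 47.2%. Per arm, 150 GPs × 50 patients = 7,500, with coefficient of variation k = 0.2 (section 10.1).

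**Step 1. Reproduce the protocol's own figures.** LR− = (1 − Se)/Sp and NPV = (1 − p)Sp / [(1 − p)Sp + p(1 − Se)].

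- Derivation: LR− = 0.024/0.713 = 0.0337 (stated 0.033). NPV = 0.88 × 0.713 / (0.88 × 0.713 + 0.12 × 0.024) = 0.6274/0.6303 = 99.5% (stated 99.5%).
- Validation: LR− = 0.144/0.472 = 0.305 (stated 0.305). NPV at 12% = 0.4154/0.4326 = 96.0%. The stated 94.8% corresponds to a prevalence of 15.2%.

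**Step 2. Share scoring 5 or more** = 1 − [(1 − p)Sp + p(1 − Se)].

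- Derivation, p = 12%: 1 − 0.6303 = 37.0%, about 2,770 of 7,500 per arm. About 4,730 remain in e).
- Validation, p = 12%: 1 − 0.4326 = 56.7%, about 4,255 of 7,500. About 3,245 remain in e).
- Validation, p = 15.2%: 57.8%, about 4,335 of 7,500.

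**Step 3. Bias if unscored CPR patients drop out of e).** Let r be the true low-risk test rate, the same in both arms (no effect of the rule). Let u be the fraction unscored in the CPR arm and r_u their test rate. The scored remainder shows (r − u·r_u)/(1 − u). All three inputs are assumptions, because the protocol gives none of them. With r = 30%:

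- u = 20%, r_u = 10%: (0.30 − 0.02)/0.80 = 35.0%, bias +5 points.
- u = 20%, r_u = 50%: (0.30 − 0.10)/0.80 = 25.0%, bias −5 points.
- u = 10%, r_u = 10%: (0.30 − 0.01)/0.90 = 32.2%, bias +2.2 points.
- u = 10%, r_u = 50%: (0.30 − 0.05)/0.90 = 27.8%, bias −2.2 points.

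If the unscored are tested at the same rate as the rest, the bias is zero.

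**Step 4. Scale.** Number of clusters per arm: c = 1 + (z_α/2 + z_β)² × [p0(1 − p0)/m + p1(1 − p1)/m + k²(p0² + p1²)] / (p0 − p1)². Take c = 150 and k = 0.2, and assume two-sided 5% and 80% power, so (1.960 + 0.842)² = 7.85. The average low-risk cluster is m = 50 × 0.630 = 31.5 (derivation) or 50 × 0.433 = 21.6 (validation). Using the overall 42% test rate from section 10.1 as p0 and the same k, the smallest detectable drop in e) is 3.9 or 4.3 points, against 3.5 points in f) with m = 50. With p0 = 30%, as in step 3, it is 3.2 or 3.6 points. Check for m = 31.5, p1 = 0.268: 1 + 7.85 × (0.00667 + 0.00623 + 0.00647)/0.032² ≈ 149.5. A 5-point bias is larger than any of these; a 2-point bias is not.

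**The case against.** **Item f) already compares the whole arms.** This stands. A reader might infer that the plan cannot show impact, or that patients at 5 or more are left out of the evaluation. Neither follows: f) includes everyone, and any rise in testing above the cut-off is netted there. Item e) is also a sensible target for a rule-out tool, and step 4 shows that it keeps most of the trial's ability to detect a difference.

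**Most patients need not score 5 or more.** This stands. A majority follows only from the external figures, and section 1.2 says that inclusion criteria differed between the Swiss and German studies. The derivation figures come from the TOPIC-based rule, and section 10.1 treats TOPIC as the same population. They give a minority.

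**Impact may only be a label.** Section 6 uses the word for a class of endpoints, and these are the rows of d). The protocol nowhere claims that the gradient is the rule's effect. This is a fair reading of the intent, but the heading still invites the wrong one.

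**Item e) may give control-arm values for all strata.** Its opening words allow this. Set beside d), both arms would then be tabulated, but the only comparison named is for low risk, and the two sides would still be scored differently.

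**The loss of unscored patients is an inference.** This is partly right. Item e) does not say which CPR-arm score it uses. Not using the score during the consultation does not mean that the total is blank, and section 10.3 tries recontact and extrapolation before exclusion. These make the loss smaller but do not rule it out. Section 3.4 takes non-use seriously enough to make it a stopping criterion. Even with every total present, a GP's total and an investigator's calculation are different measurements.

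**Conclusion.** The point holds for the secondary, score-based analyses and does not reach f). Item d) cannot show an effect of the rule. Item e) leaves about 37% (derivation figures) to 57% (external figures) of patients without a between-arm comparison by stratum. As described, e) also compares a group defined by investigators with one defined by GPs. That last fault matters most, because it can bias a comparison that randomisation would otherwise protect.

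The size of the bias is illustrative. It is about 5 points in either direction with 20% unscored and about 2 points with 10%, on assumed test rates of 30% in low-risk patients overall and 10% or 50% in the unscored. The protocol supports no single value and no direction. The conclusion also rests on reading the GP's total as the CPR-arm score in e), which is the only CPR-arm score described.

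**What to change.** - Keep f) as the main impact comparison.
- Replace d) and e) with one secondary table showing both arms in each risk stratum of the score finally chosen (below 5, 5 to 7 and above 7 for the Swiss score), with the CPR-minus-usual difference in each.
- Assign the stratum in both arms by the same investigator calculation from the common CRF items, including CPR patients for whom the GP gave no total.
- Use the GP's own total only for use and agreement in g).
- Do not head any within-arm table as impact.

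**Cost.** For the Swiss score this is a change of wording and a little more analysis. The common items approximate some score items: outside the score box, the CRF records palpation only as a trigger tick-box, so a blank does not separate absence of tenderness from no examination, and telephone contacts are eligible. That limitation should be stated; it would then apply equally to both arms. If the Marburg score is chosen, which section 5 leaves open, the strata must follow its own cut-off. The CRF text shows no field outside the score box for the patient's belief that the pain is cardiac, so such a field would have to be added for both arms.

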### 3.4 Study duration for subjects and stopping rules

The study duration is of 9 months for subjects, from index visit to end of follow-up. Study ends with routine consultation at GP's office 6 to 9 months after index visit or, if no consultation is scheduled, with telephonic interview at 9 months.

Intermediate analysis is done at 3 months and *stopping rules* are:

- The CPR is so effective that it has to be applied to control group
- There is no significant difference between intervention and control group or no data indicating that a difference may be expected at the end of complete follow-up
- Non use of the CPR by GPs of the intervention group
- Unexpected unfavourable effect on patients

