### Douleur thoracique:

**Contexte :** nouvelle  / connue  plainte principale  / plainte secondaire

**Intensité:** faible  modérée  forte

[figure not shown]
**Installation:** soudaine  progressive

**Evolution:** en augmentation  en diminution  intermittente   
constante avec exacerbations

**Durée:** <1 minute  <15 minutes  <1 heure  heures   
jours  mal défini

**Type:** superficielle  profonde  oppressante  en lancées   
brûlure

**Localisation :** rétrosternale  transfixiante  localisée  étendue

Préciser (avec irradiation si présente) :

**Facteur déclenchant:** effort  mouvement  décubitus  repas   
anxiété  palpation

**Facteur aggravant:** toux  respiration  position  déglutition   
effort

Autre(s) caractéristique(s) (préciser) : \_\_\_\_\_

**Symptômes d'accompagnement :****Général :** fièvre  frissons  sudations  altération conscience **Cardiovasculaire :** palpitation  syncope  tachycardie  arythmie   
instabilité hémodynamique   
autre  (préciser) : \_\_\_\_\_**Respiratoire :** dyspnée  toux  expectorations   
autre  (préciser) : \_\_\_\_\_**Digestif :** dysphagie  reflux  épigastralgies   
autre  (préciser) : \_\_\_\_\_**Articulaire :** préciser si présent(s) : \_\_\_\_\_**Facteurs de risque :**HTA  diabète  dyslipidémie Tabagisme  : \_\_\_\_ UPA OH  : \_\_\_\_ dl/semaineAnamnèse familiale positive Antécédents personnels cardiovasculaires (maladie coronarienne, maladie cérébrovasculaire, artériopathie périphérique) Antécédent personnel maladie thromboembolique veineuse **Score clinique cardiovasculaire (uniquement pour les médecins du « groupe CPR ») :**

Swiss Heart Score	
Men over 55 years, women over 65 years	2 points
Known cardiovascular risk	2 points
Personal history of cardiovascular disease	2 points
Substernal pain	2 points
Duration of pain from 1 to 60 minutes	1 point
Increasing with effort	1 point
No tenderness at palpation	1 point
Total < 5 points: low risk of cardiogenic chest pain	
Total 5 to 7 points: intermediate risk of cardiogenic chest pain	
Total > 7 points: high risk of cardiogenic chest pai	
- Sensitivity 97.6%, specificity 71.3%, negative likelihood ratio 0.033, negative predictive value 99,5% (derivation cohort)	
- Sensitivity 85.6%, specificity 47.2%, negative likelihood ratio 0.305, negative predictive value 94.8% (validation cohort)	

**Total :** \_\_\_\_ points

Alternativement :

Marburg Heart Score	
Men over 55 years, women over 65 years	1 point
Known clinical vascular disease*	1 point

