**Appréciation du score clinique cardiovasculaire (uniquement pour les médecins du « groupe CPR ») :**

Utilisation *au cours* de la consultation :      oui  / non

*Sinon, pourquoi ?* Oubli       inadapté       autre  (préciser) : \_\_\_\_\_

Si le résultat du score a indiqué un *risque faible* d'origine cardiaque à la douleur thoracique :

Aucun impact      0 - 1 - 2 - 3 - 4      Rassurant

Degré de satisfaction : insatisfaisant      0 - 1 - 2 - 3 - 4      très satisfaisant

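### Analysis 10.2 e) compares low-risk patients between arms, but the score that defines low risk comes from the GP in one arm and from the investigators in the other, with no rule for CPR-arm patients who have no GP total

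*Protocol*

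**What the plan says.** Section 3.5 of the protocol gives the score two sources. In the CPR arm, "GPs of the intervention group will be asked to calculate the risk of cardiogenic chest pain for each patient with the CPR". In the control arm GPs rely on clinical judgement, and "investigators will be able to calculate patients' risk of cardiogenic chest pain a posteriori in the usual care group" from the CRF. Section 10.2 e) repeats the after-the-fact calculation for the usual-practice group only and then announces a "comparison of endpoints in low risk patients of usual practice group versus CPR group". The score block of the CRF in Annex 2, with its line for the total, is marked "uniquement pour les médecins du « groupe CPR".

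Scoring is not optional in the CPR arm: under section 5 those GPs "will have to calculate the risk of cardiac origin to chest pain for each patient". Non-use is nevertheless foreseen in three places:

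- It is a stopping rule in section 3.4: "Non use of the CPR by GPs of the intervention group".
- It is an analysis in section 10.2 g): "use/non use rate of the CPR, acceptability and satisfaction".
- It is a per-patient CRF question, "Utilisation *au cours* de la consultation", with forgotten, unsuitable or other as reasons for a no.

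For missing data in general, section 10.3 sets an order: contact the GP or patient, then extrapolate, then exclude. Section 3.1 has research staff check that CRFs are complete. Neither mentions a missing score, and no section says that the investigators calculate the score in the CPR arm.

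**The concern.** Analysis e) is the only between-arm comparison confined to the patients whom the rule is meant to rule out, which is where a saving in tests should be concentrated. For a fair comparison, a patient with given characteristics must be classified the same way in either arm. Two features of the plan put that at risk.

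First, a CPR-arm patient without a GP total has no stated place in d) or e), while a comparable control patient is classified from the CRF items. If unscored patients are tested more often than scored ones, leaving them out makes the CPR arm look more sparing than it is. If they are tested less often, a real saving is hidden.

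Second, even with full use, the CPR-arm total is added up by a GP who knows it is meant to inform the decision to test (Annex 1). The control-arm score is assembled by investigators from tick-boxes. Items such as known cardiovascular risk leave room for judgement, so patients near the cut-off of 5 may fall on different sides depending on the arm.

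**Working it through.** **The plan's own total.** 300 GPs × 50 patients = 15,000, as stated in section 10.1; that is 7,500 per arm. The concern changes no stated figure.

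**How low risk arises in each arm**

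| | CPR arm | Usual practice |
|---|---|---|
| Who scores | GP | Investigators |
| When | Index visit | Afterwards |
| From what | Score block on the CRF | General CRF items |
| Without a GP total | No rule stated | Not relevant |

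**Expected size of the low-risk group.** Inputs are CHD prevalence 12% (section 1.1) and the two accuracy pairs in section 5.

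Share below 5 = (1 − sensitivity) × prevalence + specificity × (1 − prevalence)

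- Derivation cohort: 0.024 × 0.12 + 0.713 × 0.88 = 0.630, or about 4,727 patients per arm.
- Validation cohort: 0.144 × 0.12 + 0.472 × 0.88 = 0.433, or about 3,245 per arm.

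If unscored patients were excluded and non-use were 10% or 30% (assumed), the CPR-arm group would fall to 4,255 or 3,309 on the first figure, and to 2,920 or 2,271 on the second. Non-use would not shrink the control group.

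**Bias when the rule has no effect.** Let T be the true test rate in low-risk patients, equal in both arms; u the share of CPR-arm low-risk patients without a score; and g the test rate in unscored minus that in scored patients. If S is the rate in scored patients, T = S + u × g, so the apparent difference is S − T = −u × g.

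- u = 0.10, g = 10 points: 1 point.
- u = 0.30, g = 20 points: 6 points.
- g = 0 or u = 0: no bias.

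The sign follows the sign of g. Both u and g are assumptions; the protocol gives neither.

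**A second set of assumptions.** Take T = 42%, which is the all-patient rate in section 10.1 and is only assumed for low-risk patients, and u = 0.20. Let r be the test rate in unscored relative to scored patients, so that S = T / [(1 − u) + u × r].

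- r = 1.5: 0.42 / 1.1 = 38.2%, a difference of −3.8 points.
- r = 2: 0.42 / 1.2 = 35.0%, −7.0 points.
- r = 0.5: 0.42 / 0.9 = 46.7%, +4.7 points.
- r = 1: no difference.

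The range of 1 to 6 points is therefore an illustration, not a bound.

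**A yardstick.** The Hayes–Bennett formula for clusters per arm is c = 1 + (zα + zβ)² × [p0(1 − p0)/m + p1(1 − p1)/m + k²(p0² + p1²)] / (p0 − p1)². Section 10.1 gives m = 50, k = 0.2, p0 = 0.42 and 150 clusters per arm. With an assumed two-sided 5% level and 80% power, p1 = 0.385 gives 1 + 7.849 × 0.02259 / 0.001225, about 146, which is within 150. The detectable whole-arm difference is thus about 3.5 points, and about 4 points at 90% power. If all of a 3.5-point fall occurred in low-risk patients, it would be 3.5 / 0.630 = 5.6 to 3.5 / 0.433 = 8.1 points among them. The protocol's own expected intervention-arm rates are not in the text available, so these figures serve only for scale.

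No figure can be put on the difference between scorers, because the protocol gives no data on agreement between GP and investigator scores.

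**The case against.** The best defence is that the protocol requires a score for every CPR-arm patient, checks CRFs for completeness and tries to recover missing data before excluding anyone. The after-the-fact calculation is mentioned for the control arm because no score would otherwise exist there, and which score defines a subgroup is often left to the SAP.

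Much of this stands, and it rules out three stronger readings.

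- A reader might infer that CPR-arm GPs choose whom to score. Sections 3.3, 3.5 and 5 contradict this; what is left to the GP is whether to act on the result.
- A reader might infer that every patient marked as non-use drops out of the low-risk group. The CRF question concerns use during the consultation, so a GP may answer no and still enter a total, and section 10.3 makes exclusion the last step. Nor is it certain that every control patient is classified: section 3.5 says only that the calculation will be possible, and incomplete items go through the same steps.
- A reader might infer that the trial's randomised comparison fails. Analysis f) compares whole arms and does not use the score, and the sample size is set for a whole-arm difference in tests.

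What the defence does not remove is that the protocol is not silent here: it states a source for the score that depends on the arm and builds a between-arm comparison on it. Recovery under section 10.3 does not restore symmetry either. A total obtained from the GP later may be written after test results are known, and it is still a GP total.

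**Conclusion.** The point holds as a defect in how the low-risk subgroup is defined. Followed as written, sections 3.5 and 10.2 e) can classify similar patients differently by arm, and CPR-arm patients without a GP total have no stated place in d) or e). Whether the groups then differ in practice depends on how common and how selective non-use is and on how far GP and investigator scores disagree, none of which the documents show. The non-use component is 1 to 6 points in either direction under the stated assumptions and zero if non-use is unrelated to testing. Since the whole trial can detect roughly 3.5 to 4 points under the assumed error rates, bias of that order would be enough to mislead in e). Analysis f) is untouched, so this should be corrected but does not undermine the trial's main comparison.

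**What to change.** In sections 3.5 and 10.2 d) and e), state that low risk is defined in both arms by one central calculation from the index-visit CRF items common to both arms, with the same algorithm for all patients, whatever the GP's use of the score or written total. Report the GP-entered total, and its agreement with the central score, under g).

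The cost is a sentence or two in each section and one derivation program, with two caveats. The risk group analysed may differ from the one the CPR-arm GP saw; the agreement reported under g) would show how often. And tenderness needs care: outside the CPR-only block, the CRF records palpation only as a trigger of the pain, not as an examination finding. The same coding of that item must therefore be fixed in advance and applied in both arms, without drawing on the score block in the CPR arm.
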